6.5. POOLING OF CENTERS

Subjects will not be pooled based on site size, but rather by region, to ensure a sufficient number of subjects per treatment arm in both ITT and PP populations for analysis that contain region as a model effect. The table below shows which countries comprise each of the regions to be used in analysis.

Region	Country
Europe	Czech Republic
	Denmark
	Netherlands
	Poland
	Russian Federation
North America	United States
	Canada
	Mexico
Asia Pacific	Republic of Korea
	Taiwan, Province of China

7. DEMOGRAPHIC, OTHER BASELINE CHARACTERISTICS AND MEDICATION

7.1. SUBJECT DISPOSITION AND WITHDRAWALS

Subject disposition data will be listed. A disposition table will present, by treatment arm and overall, the number and/or percentage of subjects who signed the informed consent and entered the study (i.e., were screened, screen failed prior to Run-in, screen failed during the Run-in, and randomized), completed study drug through week 24, completed the study drug, withdrew from the study, completed the study, and discontinued treatment after randomization. The reasons for early withdrawal after randomization will be summarized.

Attempts will be made to collect vital status information that is allowed by local guidelines in subjects who discontinued participation in the study after randomization. The number of subjects for whom vital status has been determined will be presented.

Assignment to the analysis sets (safety, ITT, and PP) will be summarized.

All dispositions will be summarized for all subjects, subjects who has been prescribed insulin or sulfonylurea, and by subgroups: CV risk groups.

7.2. SUBJECT ELIGIBILITY AND PROTOCOL DEVIATIONS

All subjects, including screen failure subjects, who do not meet the Inclusion/exclusion criteria, will be listed. Reasons for screen failure will be summarized.

Deviations that could affect the primary and secondary variables will be considered when determining a subject's eligibility for the PP population. The number and percent of subjects who had any major deviation and each type of major protocol deviation will be tabulated for the ITT Analysis Set.

7.3. DEMOGRAPHIC AND OTHER BASELINE CHARACTERISTICS

Demographic characteristics include age, gender, race, ethnicity, country of investigational site and CV history. Baseline characteristics will include baseline HbA_{1c}, baseline HbA_{1c} categories (< 9.5% or ≥ 9.5%), baseline eGFR, baseline eGFR categories (< 60 or ≥ 60 mL min⁻¹ per 1.73 m²), blood pressure (systolic and diastolic), body weight, FPG, stratification factors recorded at screening visit in IWRS: including HbA_{1c} (< 9.5% or ≥ 9.5%), eGFR (< 60 or ≥ 60 mL min⁻¹ per 1.73 m²), body mass index (BMI < 25 kg m⁻² or BMI ≥ 25 kg m⁻²) and history of heart failure (yes or no), cardiovascular risk factors and subcategories, and type of hypertensive medication and hypoglycemic agents used by ATC class 4. Hypertensive medication includes any medication in ATC level 2 class of C02, C07, C08, C09, and C03. For Group 2 subjects, NT-proBNP values will be

determined at the screening visit in subjects who consent to participate in the study under protocol amendment 8. Ejection fraction is reported for Group 2 subjects. Ejection fraction will be summarized for Group 2 subjects.

Summary descriptive statistics by treatment will include counts and percentages for discrete variables and means, standard deviations, medians, inter-quartile range (Q1, Q3), minimum, and maximum for continuous variables. Subjects' baseline demographic and personal baseline characteristics will be summarized by treatment arm and overall for subjects in the safety, ITT, and PP analysis set. Subject age will be the age at date of informed consent collected from CRF. Summary for demographics will be repeated for region, CV groups, and tables based on safety and ITT analysis set will be repeated for insulin use and sulfonylurea use subgroups.

7.4. MEDICAL HISTORY

Significant medical and surgical history, including dates of diagnoses and procedures and whether the condition is ongoing, if applicable, will be collected. Each condition will be recorded as a verbatim term, date of onset, date resolved, and a checkbox that indicates ongoing conditions. Significant surgical and medical history will be coded using the Medical Dictionary for Regulatory Activities (MedDRA) version 18.1.

Medical and surgical history will be summarized for the Safety Analysis Set by treatment arm, system organ class (SOC), and MedDRA preferred term (PT), overall.

Subject diabetes and cardiovascular diseases history will be summarized for statistical treatment as categorical variables by frequency and percentage, for all subjects and by insulin use, sulfonylurea use.

7.5. MEDICATION

All prescription and over-the-counter medications, including vitamins and herbal supplements, that subjects receive during the trial must be documented on the CRF. The medication name, dose, frequency, route of administration, date(s) of administration and reason for administration must be recorded. This documentation should continue through the treatment period and the follow up period. Changes from baseline anti-hypertensive therapy and their rationale must be recorded in the CRF.

All medication will be coded using the World Health Organization Drug Dictionary (WHO-DD) version B2Enhanced March 2016. The preferred drug name and Anatomical/Therapeutic/ Chemical (ATC) class will be reported for inclusion in the database.

Medication summaries based on ATC level 2, and the preferred drug names will be produced for the Safety Analysis Set. The summaries will present, by treatment arm, the frequency and percentage of subjects who used any medication in an ATC class, or any medication based on a single preferred drug name. Medication summaries will be sorted by descending total frequency of ATC class and by PT within ATC class. Subjects will be counted only once for each medication class and each preferred drug name.

For subject listings, medications will be reported based on ATC class and PT; multiple medications for an individual subject will be listed by start date and then by stop date, from earliest to latest medications.

7.5.1. Prior Medication

Any medication with a start date and an end date prior to or on the first dose date for the double-blind treatment period will be considered a prior medication.

Prior and concomitant medications will be presented together on a single listing. The listing will be ordered by subject number, and medication start/end dates. Prior medication will be identified in the listing.

7.5.2. Concomitant Medication

A concomitant medication is any medication that the subject has taken in any time during the study treatment period. In the case of a missing stop date, medication will be assumed to be concomitant.

All medications must be recorded in the CRF medication log.

Concomitant medications will be presented in a summary table as well as in a subject listing.

8. EFFICACY

Efficacy data include HbA_{1c}, FPG, body weight, and blood pressure. All changes from baseline will be calculated as the post-treatment value minus the baseline value. All continuous efficacy data will be summarized for observed and change values by treatment and visit. The proportion of subjects requiring an intensification of anti-diabetic regimen, proportion of subjects requiring a relaxation of anti-diabetic regimen, incidence of and time to hospitalization for heart failure will be summarized by frequency, and the proportion by treatment and visit.

8.1. PRIMARY EFFICACY ENDPOINT AND ANALYSIS

The primary efficacy hypothesis is that bexagliflozin reduces HbA_{1c} after 24 weeks of treatment when compared to placebo.

8.1.1. Primary Efficacy Analysis

Let $\mu_{\text{Bexagliflozin}}$ and μ_{PBO} represent the mean changes from baseline in HbA_{1c} at Week 24 for bexagliflozin and placebo arms, respectively. The following hypotheses will be tested:

$$H_0: \mu_{\text{bexagliflozin}} - \mu_{\text{placebo}} \geq 0$$

$$H_a: \mu_{\text{bexagliflozin}} - \mu_{\text{placebo}} < 0$$

Missing data will be imputed via multiple imputations, following which the MMRM will be repeated on the complete datasets with results combined across complete datasets using standard multiple imputations techniques; HbA_{1c} values collected after the start of intensification of hypoglycemic agent will not be excluded. A pattern-mixture model will be used to explore the impact of the missing data. Imputation will be conducted within each treatment arm and subgroup (treatment completer vs. treatment terminated early) under the assumption that non-adherent subjects with missing data will follow the same trajectory of non-adherent subjects with values observed. All efforts will be made to retain subjects in the study. If treatment is discontinued, subjects are encouraged to remain in the study and complete all scheduled visits, including final follow-up visit. However, with all efforts, insufficient values may be available for reliable imputation. This analysis will be performed only if at least 5 subjects in each treatment arm completed scheduled week 24 visit after treatment is stopped. This number is chosen to allow sufficient data to establish a regression model for imputation. For this analysis, the following three-step approach outlined below will be used:

- a. Non-monotone (intermediate visits) missing data will be imputed first using the Monte Carlo Markov Chain (MCMC) method under the MAR assumption in all treatment arms (using the MCMC statement in PROC MI). Multiple chains option

(CHAIN=MULTIPLE option in the MCMC statement of PROC MI) will be used. For the non-monotone imputation of the HbA_{1c} missing data, a multivariate normal model will be used including variables for the HbA_{1c} at baseline and all post-baseline visits within each treatment group. Five hundred imputed datasets will be generated.

- b. After the non-monotone missing data have been imputed, the remaining monotone missing data will be imputed within each treatment arm and subgroup, defined by whether subject completed 24 week of study treatment, using regression approach. The predictors for the regression imputation model at any time point will be HbA_{1c} at all previous time points, including baseline. Imputations will be performed using a sequence of regression-based imputations (using PROC MI statement MONOTONE REG) at each post-baseline time point.
- c. Imputed data in each of the multiple imputed datasets will be analyzed using a mixed model repeated measures (MMRM) approach. The MMRM model will include treatment, visit, treatment-by-visit interaction, region, visit, treatment, treatment-by-visit interaction, baseline eGFR categories (<60 or ≥60 mL min⁻¹ per 1.73 m²), baseline BMI (< or ≥25 kg m⁻²), and history of heart failure (yes or no), insulin use or not, as fixed effects and the corresponding baseline HbA_{1c} as a fixed effect covariate. The analysis will evaluate the mean change from baseline in HbA_{1c} over the 24 week double blind treatment period. An unstructured covariance will be used to model the within subject correlation. The Kenward Roger approximation will be used to estimate denominator degrees of freedom. If the model with the unstructured covariance structure does not converge, an autoregressive(1) covariance structure will be used. HbA_{1c} values obtained after the start of intensification of hypoglycemic agent will not be excluded from the analysis. The treatment and treatment by visit interaction terms allow for comparisons of the treatment groups at each visit, and over week 6 to week 24. Least squares (LS) mean treatment differences between the bexagliflozin group and the placebo group at week 24 will be estimated from the model. The LS mean results from all imputed datasets will be combined using the Rubin's combination rule (PROC MIANALYZE).

If no sufficient week 24 values from treatment discontinued subjects are available for imputation, MMRM analysis will be performed using all available data. Method described in above step c will be utilized.

Descriptive statistics (n, mean, Q1, median, Q3, SD, minimum, and maximum) will be reported by treatment arm and all observed visits. The least squares means, differences between LS means, a 2-sided 95% confidence interval for each difference, and p-values from the model effects up to week 24 visit will be presented. In addition, the observed change from baseline for all available visits with standard errors, LS means with

standard errors of the change from baseline over time and difference between treatment arms with 95% will be presented graphically for the ITT population.

For supportive analyses, the primary efficacy endpoint will be analyzed with observed available data using the PP analysis set in a similar manner as above.

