7.5 Discontinuation of Investigational Product Administration

Subjects who discontinue the investigational product administration early but are willing to remain in the study to allow safety information to be collected should complete the End of Treatment visit procedures. Safety data may be documented following the scheduled clinic visit and/or phone interview procedures as much as possible without the study drug

dispensation and accountability procedures. Alternative follow up methods to allow safety assessment to be recorded may be implemented as unscheduled visits.

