6.4. ANALYSIS VISIT WINDOWS

Table 6 shows how data will be mapped to visit number prior to selection of records for analysis. All post-baseline visits, including unscheduled and early termination visits, will be mapped.

After mapping the data to the visits, the following rules will apply unless other handling is specified for a particular analysis.

- If multiple records are available within a single visit window, the record closest to the planned assessment day will be selected for analysis.
- If 2 records are equidistant from the target day, then the later record will be selected.
- If a subject has no record in an analysis window, the data will be considered missing at that visit.

Table 6 Analysis Visit Windows

Study Day Window	Scheduled day	Scheduled Visit/Week
Day 1 - 63	Day 42	Visit 5/Week 6
Day 64 - 105	Day 84	Visit 6/Week 12
Day 106 - 147	Day 126	Visit 7/Week 18
Day 148 - 210	Day 168	Visit 8/Week 24
Day 211 - 294	Day 252	Visit 9/Week 36
Day 295 - 420	Day 336	Visit 10/Week 48
Day (xx*7-83) - minimum (xx*7+84, End of Treatment Visit date)	Day (xx*7)	Visit /Week xx, where xx is every 24 weeks.
> End of Treatment Visit date + 7	End of Treatment Visit + 28	Follow-up Visit

If there are multiple end of treatment visits, the one closest to the last dose date will be used. If multiple records are equidistant from the last dose date, the later one will be used. Analysis visit windows will be used for all lab, vital sign, and ECG data.

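### The primary imputation may run on 5 retrieved dropouts per arm, but its Week 24 regression has 4 coefficients, so a cell with exactly 5 values keeps 1 residual degree of freedom and most of the power is lost

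*Combined protocol and SAP*

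**What the plan says.** SAP Section 8.1.1 sets the condition for the primary analysis: "This analysis will be performed only if at least 5 subjects in each treatment arm completed scheduled week 24 visit after treatment is stopped". It gives the reason for the figure: "This number is chosen to allow sufficient data to establish a regression model for imputation".

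Step b defines the model. Remaining monotone missing values are "imputed within each treatment arm and subgroup, defined by whether subject completed 24 week of study treatment", and "The predictors for the regression imputation model at any time point will be HbA_{1c} at all previous time points, including baseline". Five hundred imputed datasets are analysed by MMRM and combined by Rubin's rule. The fallback is: "If no sufficient week 24 values from treatment discontinued subjects are available for imputation, MMRM analysis will be performed using all available data".

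Three other provisions affect how many Week 24 values a cell holds:

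- SAP Section 6.4: "All post-baseline visits, including unscheduled and early termination visits, will be mapped". Table 6 sets the Week 24 window at Day 148–210.
- Protocol Section 7.5: subjects who stop the product but are "willing to remain in the study to allow safety information to be collected should complete the End of Treatment visit procedures".
- SAP Section 8.1.1 step a fills intermediate gaps with a multivariate normal model "including variables for the HbA_{1c} at baseline and all post-baseline visits within each treatment group".

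**The concern.** The minimum of 5 is justified as enough data to establish a regression, yet the regression specified in the next step nearly exhausts 5 observations. No other figure is offered for what counts as sufficient, so nothing in the text sends a count of 5, 6 or 7 to the MMRM fallback.

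The condition also counts completed visits, whereas the regression uses HbA1c values mapped to the Week 24 window. The two counts can differ.

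This is the primary test, and under SAP Section 8.2.1 it gates every key secondary endpoint. If either arm sits at the minimum, a real effect would usually be missed and the reported standard error would depend on the seed.

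**Working it through.** **Inputs from the documents.** 1100 active and 550 placebo; effect 0.22%; SD 1.1%; stated power 90% (protocol Section 9.2). One-sided 0.025 (SAP Section 6.1). Early termination 6.5% a year (SAP Section 8.1.2). M = 500 (SAP Section 8.1.1). HbA1c before Week 24 is scheduled at Weeks 0, 6 and 12 (protocol Appendix 2); Week 18 is a phone contact.

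**The plan's own power figure.** SE = 1.1 × √(1/1100 + 1/550) = 0.0574. Power = Φ(0.22/0.0574 − 1.96) = Φ(1.87) = 96.9%. The stated 90% does not reproduce. It errs on the safe side and is a separate matter. The benchmark here is about 97%.

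**Degrees of freedom.** Intercept + baseline + Week 6 + Week 12 = 4 coefficients, so residual df = n − 4: 1 at n = 5, 2 at 6, 3 at 7, 4 at 8.

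**Why 1 df matters.** Each imputation draws σ*² = SSE/χ²(df). The mean of 1/χ²(df) is 1/(df − 2), which is finite only for df above 2, that is n ≥ 7. The draws feed the between-imputation variance B in Rubin's total, T = U + (1 + 1/M)B.

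**Missing values (derived).** 1 − 0.935^(168/365.25) = 3.04%, about 33 of 1100 and 17 of 550.

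**Simulation.** Sequential regression imputation within each arm's cell, M = 500, Rubin's rules, and a baseline-adjusted Week 24 ANCOVA standing in for the MMRM. Assumptions not in the documents:

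- Dropout timing: a quarter of those missing are missing from Week 6, a quarter from Week 12, and half at Week 24 only.
- Three sets of SDs (baseline, Weeks 6, 12 and 24) and visit correlations: 0.95/1.05/1.12/1.20 with 0.50–0.80; 1.0/1.0/1.0/1.05 with 0.62–0.85; 0.88/0.92/0.95/0.97 with 0.30–0.60. The SD of change is 1.10, 0.90 and 1.10.
- 1,500 trials per main scenario (Monte Carlo SE at most 1.3 points).

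The table also covers runs under other assumptions, including SD of change 1.1 with a common visit correlation of 0.7 and 34/17 missing (500 trials each).

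| Week 24 donor values | Residual df | Power at 0.22 |
|---|---|---|
| Complete data | – | 97–99.9% |
| 5 per arm | 1 | 0.4–3.4% |
| 5 in one arm, 10 or 20 in the other | 1 in one arm | 12–20% |
| 6 per arm | 2 | 66–85% |
| 7 per arm | 3 | 89–99% |
| 8 per arm | 4 | 93–99.7% |
| 10 per arm | 6 | 96–99.9% |

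At 5 per arm the median pooled SE is about 0.8–1.1, so 0.22/SE is only 0.20–0.28 against a critical value near 1.96. Even at 0.79%, the Week 24 effect cited in protocol Section 3.3.2, power at 5 per arm is 17–27%.

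**Other missing counts at 5 per arm.** 3/2 missing: 18%. 17/8: 3–6%. 55/28: 1%. 66/34: about 2%. With 66/34 missing, 8 per arm gives 88–98% and 10 gives 93–99%.

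**Seed dependence** (80 data sets, 10 seeds each). The ratio of largest to smallest SE on the same data is about 22 at 5 per arm, 1.6 at 6 and 1.03 at 8. At 6 per arm the verdict changed between seeds in 42–50% of data sets.

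**Null rejection, one-sided.** At most 0.1% at 5 per arm, 0.3% at 6, 1.2–1.3% at 7 and 2.2% at 8.

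**Extra donors.** The scheduled Week 24 day is Day 168. A subject who stops on Day 148–167 and attends an End of Treatment visit supplies a Week 24 value without having completed 24 weeks of treatment. Expected numbers: (0.935^(147/365.25) − 0.935^(167/365.25)) × 1100 = 3.9 active, and 2.0 placebo. If these add to a count of 5 per arm, power is 95–99.5% if all attend (9/7 donors), 80–93% if half do (7/6), and 13–20% if only the active ones do (9/5). If step a draws on Weeks 36 and 48 and fills later returners, 1, 2 or 3 extra donors per arm give 69–87%, 93–99% or 97–99.9%.

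**The case against.** The strongest reply is that the harm sits at nearly one integer. Power is mostly restored by 7, and the documents attach no likelihood to 5. If donor counts were Poisson with the active mean twice the placebo mean (an assumption), the chance that the gate opens with the smaller cell at exactly 5 would peak near 18% (placebo mean 5), fall to about 9% at mean 8 and 1% at mean 12. Exactly 5 in both arms would never exceed about 2%. This stands as a limit on probability. It does not rescue the stated reason for choosing 5, and one thin arm is enough.

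Second, window mapping can put more than 5 values in a cell. That also stands. But the calculations above use fixed counts: with an average of one extra placebo donor, none would appear about 37% of the time (e^−1).

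Third, the condition is only necessary, and the fallback refers to insufficient values, which leaves room for judgement. Yet 5 is the only figure given, and judging sufficiency later is what a prespecified gate should prevent.

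Fourth, the SAP's Version 1.3 history shows covariates were already dropped from these imputation models because subjects were too few. That shows awareness, and equally that sparse cells were a live concern. The predictors that remain still use up the minimum.

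Finally, the risk falls on power rather than false positives, and a supportive per-protocol analysis of observed data remains. True, but that analysis does not replace the primary test or open the hierarchy.

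**Conclusion.** The concern holds. With exactly 5 observed Week 24 values in an arm's early-terminator cell, the specified regression has 1 residual degree of freedom. That follows from the SAP's text and needs no assumption. Its consequence, power of 0.4–3.4% with both arms at 5 and 12–20% with one, rests on assumed correlations, missing counts and dropout timing, and on ANCOVA in place of the MMRM. The collapse appeared in every setting tried.

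The conclusion is conditional on the donor count. No retrieval rate is stated, and extra donors from window mapping or step a can shrink or remove the loss. It should be fixed because it affects the primary test and is cheap to correct.

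**What to change.** Before unblinding, state in SAP Section 8.1.1:

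1. The gate is the number of observed Week 24 HbA1c values in each arm's early-terminator cell after Section 6.4 mapping, not completed visits.
2. The three-predictor model needs at least 8 such values per arm, twice its coefficients. This is a rule of thumb; 10 is more cautious if more values are missing.
3. If either arm has 5 to 7, the Week 24 step in both arms uses only the last previous HbA1c (Week 12, observed or imputed) as predictor.
4. Below 5, the stated MMRM fallback applies.

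The choice depends on counts only, not outcomes. At 5 per arm, item 3 gave 93–99.7% power with null rejection of 1.0–1.6%. Power was 92–99.6% if active discontinuers lose the whole 0.22 effect by Week 24, and 81–95% with 66/34 missing.

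Also list the imputation time points as baseline and Weeks 6, 12 and 24. Table 6 has a Week 18 window (Day 106–147), and a Week 18 predictor would be a fifth coefficient, leaving 5 − 5 = 0 df at 5 donors. Say whether step a uses visits after Week 24.

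The cost is SAP wording, plus a simpler imputation model when few dropouts are retrieved.
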